7. STUDY PRODUCTS

7.1 LIPIFLOW THERMAL PULSATION SYSTEM

The LipiFlow® Thermal Pulsation System is a prescription device with an indication for use for the application of localized heat and pressure therapy in adult patients with chronic cystic conditions of the eyelids, including meibomian gland dysfunction, also known as evaporative dry eye or lipid deficiency dry eye. The LipiFlow is used by a physician in an in-office procedure to provide controlled heat to the inner eyelid surface and intermittent pressure to the outer eyelid to facilitate release of lipid from the cystic glands.

The LipiFlow has been cleared under pre-market notification (K161357) to market the device in the U.S (Class II device). The LipiFlow is in commercial distribution based upon a determination by the FDA that the device is substantially equivalent to a legally marketed device. In addition, the use of the device in this study is in accordance with the cleared indication for use in the commercial product labeling. The risk assessment supports that the use of the LipiFlow in this post-market study is non-significant risk because the device is designed to control the application of heat and pressure within a safe range and time. Thus, this post-market study is an exempted investigation under 21 CFR 812.2(c)(2).

7.2 INTRAOCULAR LENSES

The lens models to be used in this study are the commercially-available Symphony IOLs. The TECNIS Symphony Extended Range of Vision Intraocular Lenses (IOLs), lens model ZXR00 and toric lens models ZXT150, ZXT225, ZXT300, and ZXT375, are ultraviolet light-absorbing posterior chamber IOLs which are intended to mitigate the effects of presbyopia and provide a continuous range of high-quality vision by extending the depth of focus.

The TECNIS Symphony® Extended Range of Vision IOL, Model ZXR00, is indicated for primary implantation for the visual correction of aphakia, in adult patients with less than 1 diopter of preexisting corneal astigmatism, in whom a cataractous lens has been removed. The lens mitigates the effects of presbyopia by providing an extended depth of focus. Compared to an aspheric monofocal IOL, the lens provides improved intermediate and near visual acuity, while maintaining comparable distance visual acuity. The Model ZXR00 IOL is intended for capsular bag placement only.

The TECNIS Symphony® Toric Extended Range of Vision IOLs, Models ZXT150, ZXT225, ZXT300, and ZXT375, are indicated for primary implantation for the visual correction of aphakia and for reduction of residual refractive astigmatism in adult patients with greater than or equal to 1 diopter of preoperative corneal astigmatism, in whom a cataractous lens has been removed. The lens mitigates the effects of presbyopia by providing an extended depth of focus. Compared to an aspheric monofocal IOL, the lens provides improved intermediate and near visual acuity, while maintaining comparable distance visual acuity. The Model Series ZXT IOLs are intended for capsular bag placement only.

8. STUDY POPULATION

All study subjects will be enrolled from the normal surgical cataract population with bilateral mild to moderate MGD, scheduled for bilateral cataract surgeries with Symphony IOL implantation, at up to 7 sites in the U.S.A. Approximately 140 subjects will be randomized and bilaterally implanted, to achieve approximately 110 evaluable subjects (55 in the study arm and 55 in the control arm).

This study will include mild to moderate MGD subjects scheduled for bilateral primary phacoemulsification cataract extraction and Symphony IOL implantation and who meet all the study inclusion and exclusion criteria in both eyes. All subjects who meet the inclusion/exclusion criteria will be offered enrollment in the study. Eligibility criteria may not be waived by the investigator. Any questions regarding patient eligibility are to be discussed with JJSV prior to subject enrollment. Those subjects who meet the inclusion/exclusion criteria and agree to participate will be randomized to either the Study group or the Control group and will be bilaterally treated with the LipiFlow

system. The subjects will be enrolled at each site sequentially until the recruitment goals are met or the site limit is reached. To minimize bias, each investigator will manage subject enrollment at his/her site to the extent possible to achieve an even distribution with respect to age among the study groups.

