8.1 INCLUSION CRITERIA

Note: All criteria apply to each study eye.

- Minimum 22 years of age.
- Bilateral cataracts for which phacoemulsification extraction and implantation with Symfony IOLs have been planned.
- Evidence of MGD in both eyes based on assessment of meibomian glands of the lower eyelid with a total meibomian gland secretion score of ≤ 15 (on a scale of 0 to 45) for each eye.
- None to moderate dry eye symptoms with questionnaire total scores between 0 and 15 on the Standard Patient Evaluation of Eye Dryness (SPEED) questionnaire^{xxii}.

Note: In each site, there should be no more than 30% enrolled subjects with none dry eye symptoms.

- Clear intraocular media other than cataract in each eye.
- Availability, willingness, ability and sufficient cognitive awareness to comply with the study protocol including: randomization; examination procedures; completion of planned bilateral cataract surgeries; compliance with no use of other MGD or dry eye treatments (except over-the-counter artificial tears, ocular lubricants, ointments, emollients or ω -3 dietary supplements) during the study; and attendance of all study visits.
- Ability to understand, read and write English to consent to study participation and complete study questionnaires.
- Willingness to sign informed consent and HIPAA authorization or equivalent documentation necessary to comply with applicable privacy laws pertaining to medical treatment in the governing country.

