10. EXPERIMENTAL PLAN

10.1 OVERVIEW

This study will be conducted in accordance with U.S. Code of Federal Regulations, the Declaration of Helsinki, ISO 14155 and all other applicable laws and regulations. The study will not begin until IRB approvals have been obtained.

This study will be a post-market, prospective, multicenter, bilateral, randomized, open-label, cross-over, comparative clinical study conducted at up to 7 sites in the U.S. Approximately 140 subjects will be randomized and bilaterally implanted, resulting in approximately 110 evaluable subjects (55 in the study arm and 55 in the control arm).

After signing the informed consent, subjects meeting all inclusion and exclusion criteria will be randomized to either the Study group or the Control group.

The duration of study participation is from the initial Preoperative Visit #1 to a final visit at 3 months or 4 months after the second-eye cataract surgery, depending upon the subject's randomized group assignment. All subjects in both arms are intended to have bilateral cataract surgery. The subjects randomized to Study group will undergo preoperative LipiFlow treatment and the subjects randomized to Control group will not receive preoperative LipiFlow treatment. Three months postoperatively, both groups will be evaluated for clinical outcomes and the Control group will receive LipiFlow treatment as the cross-over group. The Control group will be evaluated at 4 months postoperative for clinical outcomes.

Key data collection for all subjects/eyes includes distance visual acuities, manifest refraction, contrast acuity, keratometry, biometry, corneal topography, visual symptoms, Meibomian gland evaluation, biomicroscopic slit-lamp findings, complications and adverse events. A chart summary of all examination or treatment procedures required at each study visit is provided in **Appendix B**. If needed, specific equipment necessary to perform the required procedures will be supplied for the duration of the study (**Appendix C**). The study visit schedule is described in Section 10.2.

Although the study is not masked, to maintain consistency, it is recommended that a single individual (study technician or coordinator designated by the investigator) conduct all study-related vision testing, although a back-up person should also be designated and trained.

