10.3 PREOPERATIVE VISIT #1 PROCEDURES

The procedures in Preoperative Visit #1 include Informed Consent, Screening & Baseline Exam, Randomization & Enrollment. These procedures must be done in the order shown below.

Informed Consent

The Investigator or designee identifies potential study participants by reviewing medical records of patients who are planning to have bilateral cataract surgery. Potential study participants are scheduled for the initial preoperative visit.

At the initial visit, the Investigator or designee conducts the informed consent discussion and explains the study purpose, procedures, benefits, risks, discomforts, precautions and subject responsibilities to the potential study participant. The Investigator may provide written delegation of authority to a trained and qualified study staff member (e.g., study coordinator, technician) to conduct the consent discussion; however, the Investigator should be available to answer the subject's questions, as needed.

Once the Investigator or designee has answered all the subject's questions to the subject's satisfaction and the potential study participant has voluntarily agreed to participate in the study, written informed consent is obtained using the IRB-approved informed consent document. The subject and the person conducting the consent discussion (Investigator or designee) print their names, sign and date the consent.

All subjects enrolled in the study must sign the current IRB-approved informed consent document. The informed consent must be signed before any study-specific examinations are performed, and this must be documented in the source documents. An Authorization for Use/Disclosure of Health Information Form (HIPAA authorization) or similar medical treatment privacy law documentation must also be signed.

The Investigator maintains the signed informed consent document and the signed authorization form as a permanent part of the subject's medical records and provides a copy of the consent to the subject. The Investigator or designee documents in the medical records that informed consent was obtained prior to any study-specific procedures and a copy of the signed consent was given to the subject.

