Randomization ensures subjects are assigned with an equal probability to the Study or Control groups without the subject or Investigator knowing which group the subject will be assigned to until after the subject has completed the baseline exam.

Randomization helps to reduce any differences between Study and Control groups in baseline characteristics.

A randomization list has been created by the JJSV biostatistician and uploaded into the electronic data collection (EDC) system. Subjects will be randomized on a 1:1

basis to receive the LipiFlow treatment preoperatively (Study group) or after the 3-month postoperative visit (Control group). The randomization is stratified by site and blocked to reduce the imbalance between the number of subjects in the Study and Control groups. Randomization will take place after the subject has signed the informed consent document and has met all the inclusion/exclusion criteria. Once a subject has met the eligibility criteria, the site will access the EDC system to determine the randomization assignment.

If the subject is randomized to the Study group, the subject is scheduled for the LipiFlow treatment on the same day or within 1 week of the Preoperative Visit #1. If the subject is randomized to the Control group, the subject is scheduled for the second preoperative visit 2 - 4 weeks after Visit #1.

All subjects who sign an informed consent document and have been evaluated as eligible for the study enrollment will be documented on the Screening and Enrollment Log. A subject who does not meet the eligibility criteria or who chooses to discontinue study participation prior to randomization is documented on the Screening and Enrollment Log as "Not Enrolled" along with the reason. All subjects who undergo randomization are documented as "Enrolled" on the Screening and Enrollment Log and are assigned a subject identifier.

LipiFlow Treatment

The preoperative LipiFlow treatment is only applicable and required for the subjects in the Study group. It can be performed on the subjects on the same day or within 1 week of the Preoperative Visit #1.

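### Protocol section 8 asks investigators to manage enrolment for even age between arms, in tension with its own all-eligible, sequential rules and with little sound means of doing it (minor)

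*Protocol*

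**What the plan says.** Three statements stand close together in Protocol section 8, before the criteria lists:

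- Offer: "All subjects who meet the inclusion/exclusion criteria will be offered enrollment in the study".
- Order: "The subjects will be enrolled at each site sequentially until the recruitment goals are met or the site limit is reached".
- Age: as a safeguard against bias, investigators are told to "manage subject enrollment at his/her site to the extent possible to achieve an even distribution with respect to age among the study groups".

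Protocol section 10.3 describes how subjects enter and how the arm is set:

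- Candidates: "The Investigator or designee identifies potential study participants by reviewing medical records of patients who are planning to have bilateral cataract surgery", and those candidates are then scheduled for the first visit.
- List: a sponsor statistician prepared it, and "The randomization is stratified by site and blocked". Age is not named as a factor, and no block size is given.
- Assignment: after eligibility is confirmed, "the site will access the EDC system to determine the randomization assignment".
- Concealment: neither the subject nor the investigator is to know the arm until the baseline examination is complete.
- Balance: reducing baseline differences between the groups is described as a function of randomization.

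Protocol section 10.1 adds "Although the study is not masked". SAP section 3.2 tabulates age by arm. Neither document states an age-adjusted analysis.

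**The concern.** An investigator who offers enrolment to every eligible patient, in the order in which they arrive, has almost nothing left to manage. The investigator does not choose the arm, and the list that does takes no account of age. What remains is discretion over which patients are picked out at chart review and when they are brought in.

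To move age balance between arms appreciably, that discretion has to respond to the arms: who has already gone where, or who is likely to go where next. Responding in this way works against the concealment that section 10.3 sets out. At stake is a sentence meant to reduce bias that instead gives a site a protocol-based reason for choosing or timing entry in an open-label trial.

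Such choices would be hard to see afterwards. The Screening and Enrollment Log in section 10.3 covers subjects from consent onward, and no record is described of patients passed over at chart review.

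**Working it through.** The plan gives no figure on this point. The check is a reading of the passages together, followed by illustrations that rest on stated assumptions.

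**1. What the investigator can influence**

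| Step | Who controls it | Uses age? |
|---|---|---|
| Chart review and scheduling (10.3) | Investigator or designee | Only if the investigator chooses to |
| Offer of enrolment (8) | Fixed: all eligible subjects | No |
| Order of enrolment (8) | Fixed: sequential | No |
| Arm (10.3) | List in the EDC system, blocked by site | No |

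Only the first row leaves room to manage, and using it for age cuts into the second or third row.

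**2. How far the next arm can be guessed**

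Block size is not stated, so sizes 2, 4, 6 and 8 are assumed. Someone who knows the block size and the site's past assignments guesses the arm that is behind, and tosses a coin when the arms are level. In a complete block of size 2b the expected share of correct guesses is

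[b + (4^b / C(2b,b) − 1)/2] / (2b)

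- b = 1: (1 + (4/2 − 1)/2)/2 = 1.5/2 = 75.0%
- b = 2: (2 + (16/6 − 1)/2)/4 = 2.833/4 = 70.8%
- b = 3: (3 + (64/20 − 1)/2)/6 = 4.1/6 = 68.3%
- b = 4: (4 + (256/70 − 1)/2)/8 = 5.329/8 = 66.6%

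Enumerating all blocks gives the same shares. With 20 subjects at a site, the last block of 8 is incomplete and the share is 64.7%. This predictability exists with or without the sentence.

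**3. Age imbalance if nothing is managed**

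The standard error of the age difference, in units of the age SD, is sqrt(2/n). At the planned 69 per arm (Protocol 20.5), sqrt(2/69) = 0.170, and 1.96 × 0.170 = 0.33. The chance range is therefore about ±0.33 SD.

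**4. What age-evening would achieve, and whether it distorts the test**

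Simulation assumptions: 7 sites of 20 subjects (140 in all), no treatment effect, one value per subject, a one-sided two-sample t-test at 0.05, and 10,000 runs per scenario. The site picks, from 3 waiting patients, the one whose age brings the guessed arm's mean closest to the other arm's.

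| Situation | SD of between-arm age difference (age-SD units) |
|---|---|
| No management | 0.17 |
| Age-evening, blocks of 4 | 0.05 |
| Age-evening, blocks of 8 | 0.08 |
| Age-evening, next arm not guessable | 0.15 |

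Most of the gain disappears when the next arm cannot be guessed. For correlations of 0, 0.2 and 0.4 between age and acuity, the type I error was 0.051, 0.046 and 0.038 in blocks of 4, and 0.051, 0.048 and 0.039 in blocks of 8. None of these shows inflation.

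**5. A route that ignores the arms**

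A site could schedule similar-aged patients next to each other, so that each block compares like with like. With 3 waiting patients, the SD of the age difference falls from 0.17 to between 0.12 and 0.15 in blocks of 4, and to 0.15 or 0.16 in blocks of 8, depending on the queue rule. The gain is modest, and the order of arrival is still altered.

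**The case against.** The strongest reply is that the instruction is soft. It asks for age balance only as far as possible, so it can be read as yielding to the firm rules beside it. That stands in part. A reader might infer a strict contradiction, and the wording does not support one. What remains is an instruction in tension with its neighbours, with no statement of which gives way.

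Second, section 10.3 expressly conceals the arm until baseline is complete, and nothing in the documents allows past allocations to be used. That also stands. Use of allocations is an inference from how the sentence would have to work, not something the text permits. Blocking within site in an unmasked trial does, however, leave the next arm partly predictable.

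Third, there is an innocent route: scheduling similar-aged patients together uses no allocation information and refuses no one. This is correct, but the gain is modest and the sequence changes.

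Fourth, a reader might infer that the sentence biases the acuity comparison or raises its false-positive rate. The documents do not support this. Age-evening done as the sentence asks showed no inflation. Inflation would require deliberate selection on prognosis, which is possible in an open-label trial blocked by site whether or not the sentence is there. Error rates for such selection are not attributable to this text and are left out.

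Finally, the limit in section 8.1 ("In each site, there should be no more than 30% enrolled subjects with none dry eye symptoms") might be cited as a further conflict with the all-eligible rule. It is a note within the inclusion criteria, so section 8 can be read as including it, and it does not depend on arm.

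**Conclusion.** The point holds as a minor one. Section 8 gives investigators a balancing task that its own enrolment rules leave little room for, and that the allocation system gives them no sound tool to carry out. Apart from modest gains from grouping similar ages, the task succeeds appreciably only to the extent that allocation is known or guessed. The cost is a possible weakening of concealment, through a protocol-based reason for discretionary entry. No bias in the acuity result has been demonstrated, and nothing shows that selection would occur.

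The figures depend on assumed block sizes, on 20 subjects at each of 7 sites, on 3 patients waiting at every entry, and on one value per subject. The simulated error rates therefore do not carry over directly to the plan's all-eyes analysis: Protocol 20.1 and SAP 2.1 acknowledge correlation between a subject's eyes but state no adjustment for it in the test. The reading of the passages does not depend on these assumptions.

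**What to change.** Delete the section 8 sentence that contains the age instruction, and leave baseline balance to randomization, as section 10.3 already does. Keep the all-eligible, sequential rule, and state that it is subject to the section 8.1 criteria, including the 30% site limit on subjects without dry eye symptoms.

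If age balance matters to the sponsor, handle it in the analysis: prespecify one age-adjusted analysis of 3-month UCDVA that allows for two eyes per subject. It would address age only, not selection on other prognostic factors.

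The cost is one sentence deleted and one clause added. The optional analysis needs one SAP paragraph and one table, and uses age, which is already collected. No new visits, data or subjects are needed. The downside is that chance age imbalance, with a standard error of about 0.17 SD at 69 per arm, is no longer informally managed at recruitment. The change needs the amendment approvals: Protocol section 12, which concerns changes requested by investigators, names the FDA and other regulators as well as IRBs. It is best folded into the next amendment.

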8.1 INCLUSION CRITERIA

Note: All criteria apply to each study eye.

- Minimum 22 years of age.
- Bilateral cataracts for which phacoemulsification extraction and implantation with Symfony IOLs have been planned.
- Evidence of MGD in both eyes based on assessment of meibomian glands of the lower eyelid with a total meibomian gland secretion score of ≤ 15 (on a scale of 0 to 45) for each eye.
- None to moderate dry eye symptoms with questionnaire total scores between 0 and 15 on the Standard Patient Evaluation of Eye Dryness (SPEED) questionnaire^{xxii}.

Note: In each site, there should be no more than 30% enrolled subjects with none dry eye symptoms.

- Clear intraocular media other than cataract in each eye.
- Availability, willingness, ability and sufficient cognitive awareness to comply with the study protocol including: randomization; examination procedures; completion of planned bilateral cataract surgeries; compliance with no use of other MGD or dry eye treatments (except over-the-counter artificial tears, ocular lubricants, ointments, emollients or ω -3 dietary supplements) during the study; and attendance of all study visits.
- Ability to understand, read and write English to consent to study participation and complete study questionnaires.
- Willingness to sign informed consent and HIPAA authorization or equivalent documentation necessary to comply with applicable privacy laws pertaining to medical treatment in the governing country.

8.2 EXCLUSION CRITERIA

Note: All criteria apply to each study eye.

- Any medical finding that would predictably result in a postoperative best corrected distance visual acuity worse than 20/30 in either eye.
- Use of systemic or ocular medications that, in the opinion of the investigator, may affect vision or impact pupil dilation or iris structure.
- Irregular corneal astigmatism.

- Any clinically-significant corneal pathology / abnormality other than regular corneal astigmatism.
- Any clinically-significant pupil abnormalities (non-reactive, fixed pupils, or abnormally-shaped pupils).
- Subjects with conditions associated with increased risk of zonular rupture, including capsular or zonular abnormalities that may lead to IOL decentration, including pseudoexfoliation, trauma, or posterior capsule defects.
- Unwillingness or inability to stop wearing contact lens at least two weeks prior to the baseline visit.
- Known ocular disease or pathology that, in the opinion of the investigator, may affect visual acuity or require surgical intervention during the study (macular degeneration, cystoid macular edema, diabetic retinopathy, uncontrolled glaucoma, etc.).
- Systemic disease condition that causes dry eye (e.g., Stevens-Johnson syndrome, vitamin A deficiency, rheumatoid arthritis, Wegener's granulomatosis, sarcoidosis, leukemia, Riley-Day syndrome, systemic lupus erythematosus, Sjögren's syndrome).
- Unwillingness or inability to abstain from the use of systemic medications known to cause dryness (e.g., isotretinoin (Accutane®)) for the study duration. Subjects must have discontinued these medications for at least 1 month prior to the Baseline Visit measurements.
- Unwillingness or inability to abstain from the use of systemic antihistamines:
 - at least two weeks prior to the baseline Preoperative Visit #1 measurements through Preoperative Visit #2, or per site standard of care for cataract surgery, whichever is longer; and
 - at least 2 weeks prior to the Month 3 measurements; and
 - at least 2 weeks prior to the Month 4 measurements (Control group only)
- Unwillingness or inability to abstain from use of prescription medications (e.g., lifitegrast (Xiidra) for treatment of MGD or dry eye. Subjects must have discontinued using prescription medications for MGD or dry eye at least 1 month prior to the baseline Preoperative Visit #1 measurements.
- Any of the following ocular (eye or eyelid) conditions in either eye within 3 months prior to the LipiFlow treatment visit:
 - Prior intraocular, oculoplastic, corneal or refractive surgery procedure (LASIK, LASEK, RK, PRK, etc.).
 - Ocular trauma.
 - Ocular Herpes simplex or Herpes zoster (eye or eyelid) infection.

- History of recurrent ocular inflammation (e.g., retinitis, macular inflammation, choroiditis, uveitis, iritis, scleritis, episcleritis, keratitis).
- Punctal plug insertion or punctal occlusion.
- Any of the following active ocular (eye or eyelid) conditions in either eye at the baseline Preoperative Visit #1 measurements:
 - Active ocular infection (e.g., viral, bacterial, mycobacterial, protozoan or fungal infection of the cornea, conjunctiva, lacrimal gland, lacrimal sac or eyelids including hordeolum/stye).
 - Active ocular inflammation (e.g., retinitis, macular inflammation, choroiditis, uveitis, iritis, scleritis, episcleritis, keratitis).
 - Moderate to severe (Grade 2-4) allergic, vernal or giant papillary conjunctivitis
 - Severe (Grade 3 or 4) inflammation of the eyelid (e.g., blepharochalasis, staphylococcal blepharitis or seborrheic blepharitis).
 - Eyelid abnormalities that affect lid function (e.g., entropion, ectropion, tumor, edema, blepharospasm, lagophthalmos, severe trichiasis, severe ptosis).
 - Ocular surface abnormality that may compromise corneal integrity (e.g., prior chemical burn, recurrent corneal erosion, corneal epithelial defect, Grade 3 corneal fluorescein staining, or map dot fingerprint dystrophy).
- Concurrent participation or participation within 30 days prior to study visit in any other clinical trial.
- Planned monovision correction.
- Patient is pregnant, plans to become pregnant, is lactating or has another condition associated with the fluctuation of hormones that could lead to refractive changes.

